10.10.3.1.1. Discharge Criteria After First-Dose Cardiac Monitoring

These criteria will also be used on Day 1 Part 1, at the Week 16 visit of Part 1, first day of treatment re-initiation following the defined periods of treatment interruption, and for Day 1 Part 2 of the study.

Participants will be released from the clinical site after dosing (but no sooner than 4 hours postdose) when they fulfill the following **discharge criteria**:

- 1. Vital sign HR \geq 50 bpm
- If vital sign HR < 50 bpm, then the decrease from baseline must be < 10 bpm
- If participant is meeting the protocol pre-specified discharge criteria at Hour 4, the participant can only be discharged if the lowest HR recorded is not at Hour 4. If Hour 4 HR has the lowest value, the participant needs to be further monitored following extended cardiac monitoring on Day 1 procedures until it is confirmed the HR is on the upward trend before participant is discharged from the site. The full 4 hours of extended cardiac monitoring is not required to establish the upward trend, and participant is not required to return for additional cardiac monitoring on Day 2.
- 2. No evidence from ECG of second-degree AV block or higher
- 3. No participant-reported cardiac symptoms (eg, chest pain, dizziness, palpitations, lightheadedness, shortness of breath, or syncope)

For participants not meeting discharge criteria on Day 1:

- The blinded study medical monitor should be contacted if the participant does not meet the discharge criteria after 4 hours of extended cardiac monitoring on Day 1 (after 8 hour post dose).
- PI and the blinded study medical monitor should come to agreement on how to proceed and if it is appropriate to discharge the participant.
- Participants should have written instructions on when to return to the clinic on Day 2 and a 24-hour contact phone number to call in the event of any new or worsened cardiovascular symptoms.

Additional cardiac-monitoring data collected post Hour 4 needs to be captured on the CRFs.

Medically qualified personnel as per local clinical practice standards, experienced in interpreting ECGs may perform local ECG reads. If the machine-read is normal, not clinically significant, and the participant meets all other protocol pre-specified discharge criteria, the medically qualified site personnel can choose to discharge the participant based on the local ECG read. If, however, there is any clinical uncertainty, the site should wait for the interpretation by the Central reader prior to discharging the participant.

10.10.3.1.2. Cardiac Monitoring on Day 2 for Participants Not Meeting Discharge Criteria on Day 1 (and Week 16 + 1 day in Part 1)

Table 9 describes extended cardiac monitoring on Day 2 for participants not meeting discharge criteria at 4 hours on Day 1 (Section 10.10.3.1.1) or for participants who experienced a cardiovascular symptomatic event associated with HR reduction or clinically relevant 12-lead ECG during the 4-hour monitoring period on Day 1.

Tabla 0	Procedures to	ho Da	orformed	for Exton	dod Co	rdiac N	Janitaring	on Day 2
i ame 9.	- Procedures 10) ne re	eriorinea	ior rixien	пеп С я	ranacı	Monnoring.	OH DAV Z

Procedure	Predose	Hours 1, 2, 3 Postdose ^a	Hour 4 Postdose ^a
Blood pressure and HR	X^{b}	X ^c	X^c
derived from vital signs			
(seated position)			
12-lead ECG (supine position) ^d	X	_	X
Assess discharge criteria	_	_	X

- Measurements may be taken within \pm 15 minutes of the scheduled time. Record time of assessment.
- b Include body temperature and respiratory rate.
- c If the participant has a vital sign HR of < 50 bpm or if cardiovascular symptoms develop (eg, chest pain, dizziness, palpitations, and/or syncope associated with reduction of HR), the participant should continue to be closely monitored, including 12-lead ECGs as clinically indicated, until the Hour 4 discharge assessment. Include body temperature and respiratory rate.
- d Additional ECGs may be performed as clinically indicated.

10.10.3.2. Study Treatment Discontinuation Related to Postdose Cardiac Monitoring Study treatment discontinuation specific to postdose cardiac monitoring will occur in the following scenarios:

- Suspected intolerance associated with first dose cardiac effects Symptomatic cardiovascular events associated with first dose cardiac monitoring (e.g., chest pain, dizziness, palpitations, lightheadedness, shortness of breath, and/or syncope) associated with HR reduction or associated with clinically relevant 12-lead ECG changes at any time during the cardiac monitoring period on Day 1 or the extended cardiac monitoring on Day 2, if extended cardiac monitoring is applicable; participants with such AEs, irrespective of causality will be discontinued from the study intervention.
- Participants who have not met the discharge criteria by 4 hours postdose during the extended cardiac monitoring on Day 2 will be discontinued from the study treatment.

Participants who discontinue treatment due to first dose cardiac monitoring should return to site within 3 calendar days for ET visit that includes an ECG (in accordance with the SoA). The study medical monitor should be contacted before discontinuing a participant from study treatment.

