S1P receptor modulator-specific lymphocyte level decreases.	Dose-dependent reductions in peripheral lymphocyte counts is an expected PD effect of etrasimod. A clinically significant reduction in peripheral lymphocyte count, especially CTCAE Grade 4, may increase the risk of infections in some participants. The PD effect (lymphocyte lowering) of etrasimod is reversible following treatment discontinuation. In Arena Study APD334-201 treatment with etrasimod resulted in a dose-dependent decrease in lymphocyte count and quick reversal (within 2 – 4	Participants with conditions or risk factors related to infection or immune function will be excluded from the study. Participants will be assessed for safety including infections at regular intervals throughout the study to identify and mitigate the potential risks. In the completed Phase 2 study APD334-201, including a 12-week DB treatment period and a 52-week OLE, there were no clinically relevant safety signals related to infections.

Potential Risk of Clinical Significance	Summary of Data/Rationale for Risk.	Mitigation Strategy
	weeks) to normal levels following cessation of drug treatment, which is consistent with etrasimod clinical studies in other inflammatory conditions. Serial assessments of white blood cell count and differential will be performed in this study to assess the risk for serious and atypical infections.	Pre-defined stopping/drug interruption criteria are included in the design of this Study for CTCAE Grade 4 lymphopenia (ALC $< 0.2 \times 10^9$ cells/L).
First dose cardiac effect.	The S1P receptor modulator class of drugs is associated with an expected, on-target effect of reducing HR when first dosed. The totality of clinical data up to date in several inflammatory indications indicate that 2 mg etrasimod is well-tolerated with modest HR reduction that is maximal on the first day of dosing without major clinically relevant cardiac safety events.	Participants with elevated cardiac risk factors will be excluded from participation in the study. 4-hour first dose cardiac monitoring is included in Part 1 (Day 1 and Week 16) and Part 2 (Day 1), including for participants with etrasimod reinitiation after a temporary interruption/reinitiation. Participants with cardiac effects associated with first dose will be required to permanently discontinue study intervention.

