7. DISCONTINUATION OF STUDY INTERVENTION AND PARTICIPANT DISCONTINUATION/WITHDRAWAL

7.1. Discontinuation of Study Intervention

It may be necessary for a participant to permanently discontinue study intervention. Reasons for permanent discontinuation of study intervention include the following:

- Adverse events noted below (participants with AEs listed below, irrespective of
 causality, will be discontinued from the study intervention) NOTE: Sub bullets below
 are examples and are not intended to be an all-inclusive list.
 - Second episode of confirmed Grade 4 lymphopenia in the same participant (Protocol Sections 10.10.1, 10.10.2)
 - Repeated episode of a serious infection for the same participant (Protocol Section 10.10.2)
 - o Diagnosis of PML (Protocol Section 10.11)
 - Diagnosis of PRES (Protocol Section 8.4.8)
 - ECG changes (Protocol Section 7.1.3)
 - Suspected intolerance associated with first dose cardiac effects (Protocol Section 10.10.3.2)
 - o Malignancy (Protocol Section 8.4.8)
 - o HBV DNA above LLQ (Protocol Section 8.3.7)
 - O Active, latent, or inadequately treated TB infection (Protocol Section 8.3.5)

 PFIZER CONFIDENTIAL

 CT02 GSOP Clinical Protocol Template Phase 1.2.3.4 (01.4 pril 2022)

- o Clinically significant respiratory AE and or a decline in confirmed PFT values (FEV1 and/or FVC below 50% of the predicted values; Protocol Section 10.10.4)
- o Confirmed macular edema (Protocol Section 10.10.5)
- Drug-induced liver injury confirmed cases after all results of reasonable investigations have been received as per Protocol Section 10.5, and alternative etiology have been excluded (Protocol Section 10.10.5)
- Clinically significant safety concern as per investigator's judgement at Week 16 (Protocol Section 7.1.1)
- Death
- Lost to follow up
- Physician decision
- Pregnancy
- Protocol deviation
- Study terminated by Sponsor
- Withdrawal by participant
- Lack of Efficacy

Discontinuation of study intervention does not represent withdrawal from the study. If study intervention is permanently discontinued, the participant should remain in the study to be evaluated for safety. See the SoA for data to be collected at the time of discontinuation of study intervention and follow-up for any further evaluations that need to be completed.

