7.1.3. ECG Changes

Participants must permanently discontinue study intervention if suspected intolerance associated with first dose cardiac effects (Section 10.10.3.2).

If an ECG shows a new onset QTc interval above 500 ms during the treatment period, a repeat ECG is warranted. If this abnormal finding is confirmed, study intervention must be interrupted. Effective diagnostic and therapeutic strategies should be employed.

Reversible causes of prolonged QTc interval (eg, electrolyte abnormalities or hypomagnesemia), should be corrected as clinically indicated. When evaluating a participant with new onset QTc interval above 500 ms, referral to a cardiologist experienced in treating cardiac conduction disorders should be considered. Re-initiation of study treatment (refer to Section 10.10.3) can only be considered after all of the following have occurred:

- The QTcF interval is <450 ms (males) or <470 ms (females),
- The QTc prolongation is considered by the Investigator and confirmed by the cardiologist as not related to study intervention and likely caused by other factors,
- Individual risk-benefit is favorable (as determined by the Investigator, in agreement with the cardiologist), and
- After discussion with the Sponsor Medical Monitor.

If, after re-initiation, the QTc interval is again prolonged above 500 ms, then study intervention must be permanently discontinued.

If a clinically significant finding is identified (including, but not limited to, changes from baseline in QTcF after enrollment), the investigator or qualified designee will determine if the participant can continue in the study and if any change in participant management is needed. This review of the ECG printed at the time of collection must be documented. Any new clinically relevant finding should be reported as an AE.

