10.10.3. First-Dose Cardiac Monitoring

Cardiac monitoring following treatment initiation applies to the first dose administered in the Treatment Period (Day 1). Day 1 predose (ie, Baseline) vital signs (resting HR, BP, body temperature, and respiratory rate) will be used as the baseline measurements. The lowest predose HR measurement (by vital signs) will be used for comparison to the postdose measurement. It should be noted that in this section heart rate refers to pulse rate. Pulse rate will be collected as part of vital signs and heart rate will be collected as part of the ECG.

Cardiac monitoring is required at the Day 1 (first blinded dose) of Part 1 and Part 2 and Week 16 (first open label etrasimod dose) of Part 1 and will also be necessary to reinitiate study treatment if consecutive days of study treatment are missed as described in Section 7.1.7. These visits for cardiac monitoring should be conducted in the morning and not on a Friday or the day before a site-observed holiday. In the following sections describing first-dose cardiac monitoring, Day 1 refers to the first day of treatment in the Treatment Period, but the same procedures will also be used at the Week 16 visit in Part 1 (first open label dose) and the first day of treatment re-initiation following the defined periods of treatment interruption noted above. Day 2 refers to the subsequent dosing day.

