10.10.3.1. Cardiac Monitoring Schedule After First Dose

After the first dose of study treatment on Day 1 of Part 1 and Part 2, participants will be observed up to 8 hours. Cardiac monitoring on the first 4 hours (0H, 1H, 2H, 3H and 4H) is required for all participants. The second 4 hours (5H, 6H, 7H, and 8H) are not required and will only be performed for participants who do not meet discharge criteria at hour 4 of cardiac monitoring. The in-clinic cardiac monitoring on Day 1 will include assessments at the timepoints specified in Table 8. These criteria will also be used at the Part 1 Week 16 visit, the first day of treatment re-initiation following the defined periods of treatment interruption, and for Day 1 Part 2 of the study.

Participants who do not meet discharge criteria at 4 hours postdose on Day 1 will require extended cardiac monitoring on Day 1 (Table 8) and on Day 2, as described in Section 10.10.3.1.2.

For participants who experience a cardiovascular symptomatic event (eg, chest pain, dizziness, palpitations, lightheadedness, shortness of breath, and/or syncope) at any time during the first 4-hours postdose (ie, on Day 1), the Investigator should determine whether or not this event is associated with a HR reduction or clinically relevant change in 12-lead ECG. Participants who experience a symptomatic event associated with HR reduction or clinically relevant 12-lead ECG should be discontinued from study treatment if they meet the criteria described in Section 10.10.3.2. Participants who experience a symptomatic event that is not associated with HR reduction or clinically relevant 12-lead ECG may be discharged on Day 1 at Hour 4 postdose (at the Investigator's discretion and provided they meet the discharge criteria (Section 10.10.3.1.1), but must return to the clinic on Day 2 for extended cardiac monitoring as described in Section 10.10.3.2.

Table 8. Procedures to be Performed During the First-Dose Cardiac Monitoring Period

Procedure	Predose	Hours 1, 2, and 3 Postdose ^a	Hour 4 Postdose ^a	Day 1 Extended Cardiac Monitoring ^b
Blood pressure and HR derived from vital signs (seated position)	Xe	X°	X°	X ^c
12-lead ECG (supine position) ^d	X	_	X	X
Assess discharge criteria	_	_	X	X

- Measurements may be taken within \pm 15 minutes of the scheduled time. Record time of assessment.

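### Protocol 10.10.3.1.2 sends participants with a symptomatic first-dose cardiac event to a dosed Day 2 visit, although the stopping rule discontinues them

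*Protocol*

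**What the plan says.** Protocol 10.10.3.1.2 introduces Table 9, the Day 2 schedule, for two groups. The first is participants who fail the discharge criteria at 4 hours on Day 1. The second is "participants who experienced a cardiovascular symptomatic event associated with HR reduction or clinically relevant 12-lead ECG during the 4-hour monitoring period" on Day 1. Table 9 is timed predose, at Hours 1 to 3 postdose and at Hour 4 postdose, and Protocol 10.10.3 says "Day 2 refers to the subsequent dosing day".

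Protocol 10.10.3.2 covers symptomatic cardiovascular events accompanied by HR reduction or clinically relevant ECG change, at any time in the Day 1 monitoring or in any extended Day 2 monitoring. It concludes that "participants with such AEs, irrespective of causality will be discontinued from the study intervention".

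Four other places point the same way:

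- 10.10.3.1 says that those with a "symptomatic event associated with HR reduction or clinically relevant 12-lead ECG should be discontinued from study treatment" when they meet the 10.10.3.2 criteria. It treats symptomatic events without such a link differently: those participants may go home at Hour 4 if they meet the discharge criteria, but "must return to the clinic on Day 2 for extended cardiac monitoring as described in Section 10.10.3.2".
- 7.1 lists suspected first-dose cardiac intolerance as a reason for permanent discontinuation, citing 10.10.3.2.
- 7.1.3 says "Participants must permanently discontinue study intervention if suspected intolerance associated with first dose cardiac effects", again citing 10.10.3.2.
- 2.3.1 gives as a risk mitigation: "Participants with cardiac effects associated with first dose will be required to permanently discontinue study intervention".

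**The concern.** The same Day 1 event leads to two incompatible instructions. Under 10.10.3.2 the participant stops. Under the lead-in to Table 9 the participant comes back the next day for a schedule built around another dose. A site cannot do both.

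The rule concerned is the individual stopping rule for the acute effect of the drug class, a fall in heart rate and slowed AV conduction after the first dose. The risk table in 2.3.1 offers mandatory discontinuation as a mitigation for that effect. The conflicting sentence would re-dose the participants whom the mitigation is meant to protect. Read together with the second rule in 10.10.3.2 (stop if discharge criteria are not met on Day 2), it could be taken as permission to rechallenge and stop only on recurrence.

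**Working it through.** No formula applies to the main point, so the check is a comparison of texts.

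**Is Day 2 dosed?** Yes. 10.10.3 defines it as a dosing day and the Table 9 columns are predose and postdose.

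**Does 10.10.3.2 leave anyone with an associated event who could properly go to Day 2?** No. Section 10.10.3.1 makes discontinuation conditional on the 10.10.3.2 criteria, but the first of those criteria is this same event. Its timing is Day 1 *or* Day 2, so a Day 1 event is enough.

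**What does each section do with each kind of symptomatic participant?** The discharge criteria in 10.10.3.1.1 include absence of participant-reported cardiac symptoms, so it matters whether symptoms persist at Hour 4. Those whose symptoms resolve are assumed to meet the other discharge criteria.

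| Day 1 symptomatic event | 10.10.3.1 and 10.10.3.2 | 10.10.3.1.2 lead-in |
|---|---|---|
| Associated with HR/ECG change, resolved by Hour 4 | Discontinue | Day 2 (second group) |
| Associated, still symptomatic at Hour 4 | Discontinue | Day 2 (both groups) |
| Not associated, resolved by Hour 4 | Return on Day 2 | Not listed |
| Not associated, still symptomatic at Hour 4 | Day 2 | Day 2 (first group) |

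The first two rows are the contradiction. The third is an omission only, since 10.10.3.1 already states the return. The pattern fits a lost *not* in the second group: inserting it repairs rows 1 and 3. Row 2 would still reach Day 2 through the first group, so the insertion alone is not enough.

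**Would the study medical monitor be contacted anyway?** Contact is required before discontinuing a participant (10.10.3.2), or if discharge criteria are still unmet after 4 hours of extended monitoring on Day 1 (10.10.3.1.1 and Table 8). A row 1 participant handled under the lead-in triggers neither.

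**Cross-reference.** 10.10.3.1 cites 10.10.3.2 for the Day 2 procedure when it sends back the not-associated group. The procedure is in 10.10.3.1.2, which the same section cites correctly one paragraph earlier.

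**Reach.** The same procedures apply to Part 1 Day 1, the first open-label dose at Week 16, re-initiation after a defined interruption, and Part 2 Day 1 if the interim analysis leads to Part 2.

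**Estimand E1.** Discontinuation before the Week 16 visit makes a participant a non-responder (Protocol 9.1.1.1). About 60 participants are randomized 1:1, so 60/2 = 30 per arm. Changing one participant's status moves that arm's response rate by at most 1/30 = 3.3 percentage points, and only if the participant would otherwise have responded. This concerns Part 1 Day 1 and double-blind re-initiations. The Week 16 open-label dose and Part 2 have no estimand effect.

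**The case against.** The strongest reply is that this is a slip that sites are unlikely to act on. The 10.10.3.1.2 heading is limited to participants who fail the discharge criteria. The sentence says what Table 9 describes and does not itself order a dose. Section 10.10.3.1 comes first and gives the right disposition for both groups, and 10.10.3.2 follows Table 9 directly with the stopping rule. Cardiovascular events such as bradycardia and AV conduction delay are adverse events of special interest, to be reported promptly (8.4.8), and symptomatic bradycardia may qualify as a serious adverse event (10.7), reportable within 24 hours (8.4.1.1). Any Day 2 dose is given under observation with a predose ECG.

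It can also be said that the five sections are not five independent rules. Sections 7.1 and 7.1.3 only point to 10.10.3.2, and 10.10.3.1 is conditional on it. The wording of 2.3.1 is broader: read literally, it would also stop asymptomatic participants with a low heart rate, whom other text sends to Day 2.

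The count point stands: in substance there is one operative rule, restated once and cited twice, with a broader summary in 2.3.1. Still, all of these require this group to stop and none supports the lead-in. The safeguards lower the chance and the consequence of an error but do not remove it. A 24-hour reporting limit need not expire before the next day's dose, and reporting an event is not an instruction to withhold treatment. Section 10.10.3.1.2 is also where a site looks for the Day 2 procedure.

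**Conclusion.** The concern holds. The lead-in to Table 9 contradicts the stopping rule in 10.10.3.2, and the rest of the protocol shows that the lead-in is the part in error. A participant whose associated symptoms resolve by Hour 4 could be re-dosed without the study medical monitor being consulted beforehand.

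The case rests on participant safety alone. How many would be affected cannot be stated, because the documents give no rate of symptomatic first-dose events with HR or ECG change. The 3.3-point bound for Estimand E1 holds for any single reclassified participant in an arm of 30, and no analysis or decision rule depends on this sentence. The conclusion assumes only that a site might act on 10.10.3.1.2 as printed. The omitted group and the wrong cross-reference are lesser points.

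**What to change.** Three edits, by amendment or clarification letter:

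1. In the 10.10.3.1.2 lead-in, insert *not* before *associated* in the second group, so that it matches 10.10.3.1.
2. Add a sentence there: participants whose symptomatic event is associated with HR reduction or a clinically relevant ECG change are discontinued under 10.10.3.2 and receive no Day 2 dose, whether or not they meet the discharge criteria at Hour 4. This closes the remaining route through the first group.
3. In 10.10.3.1, change the Day 2 cross-reference for the not-associated group from 10.10.3.2 to 10.10.3.1.2.

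The cost is two wording corrections and one added sentence, with no added procedures, visits or participants.
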